### Outcomes and Data Sources:

Feasibility will be operationalized as the following dependent variables: (a) rate of refusal to participate (*expected <20%*), (b) opt outs (texted to stop receiving messages; *expected <5%*), (c) loss to follow up (*expected <20%*), (d) technological failures (frequency and proportion of text message “bounce backs”; *expected <20%*), (e) response to texting interactivity, as an indicator of engagement (*expected >80%*), and (f) time to reply to texting interactivity (*expected <15 sec*). Data for these outcomes will come directly from our mobile platform provider.

Acceptability will be based on participant feedback. We expect that participants will “*like*” messages (*>4* on a Likert scale) and find the intervention “*relatable*,” “*helpful*,” and “*engaging*,” when asked open-ended questions about the intervention. These outcomes will be determined during month 3, 2 weeks after the 10-week intervention, via phone follow up and web-based survey sent via text message link.

Efficacy The primary outcome is effective contraception initiation, defined as (1) patient self-reports initiation at phone follow up or via text or (2) there is electronic medical review (EMR) documentation of initiation. If there is a discrepancy between self-report and EMR documentation (e.g. received prescription but never started pills), we will prioritize self-report. We define “*contraception not initiated*” if noted by self-report to not have initiated or if lost to follow up and no evidence of initiation in EMR.

Similar to our cohort study, our second primary outcome is decisional conflict. This measures a participant’s level of commitment to choosing a birth control method and has been used in other contraceptive studies and is a validated scale. We are using the low literacy version to meet the needs of our adolescent population.

We will also conduct exploratory analyses to identify characteristics of participants who appear more likely to opt out of the study (allowing us to develop further retention strategies). Finally, we will examine texting response rates over time and how this relates to contraception initiation.

Secondary outcomes include follow-up to reproductive care clinics, pregnancy rates, an increase in condom use, talking to an adult about birth control, and psychosocial mediators of behavior change.

Data for secondary outcomes will also be collected via phone follow up and EMR review during month 3 and interactive text messaging at weeks 3 and 6. A baseline survey will collect information regarding demographics, reproductive and sexual history, prior medical care, and pregnancy intentions. Questions were adapted from the Youth Risk Behavioral Survey, National Survey of Family Growth, and written *de novo*.

Analysis: We will analyze both an intention-to-treat (ITT) population and per-protocol population. The ITT population will include all enrolled and randomized patients. The per-protocol population will only include participants who completed follow-up and, for those in the intervention group, excludes those who received none of the text messages. Acceptability and Feasibility: We will summarize outcomes related to feasibility and acceptability using standard descriptive statistics and conduct exploratory bivariable analyses to identify characteristics of participants who appear more likely to opt out of the study (in order to develop further retention strategies). Potential efficacy: We will calculate the absolute risk difference (ARD) between groups with exact test-based 95% confidence intervals. For the ITT analysis, the outcome for those lost to follow-up will be imputed conservatively as *contraception not initiated*. We will use the chi-square test to determine the potential effect of the intervention on contraception initiation. We will conduct exploratory multivariable logistic regression analyses to test if age group (older (18-19 years) versus younger (17 and younger)), ethnicity, race, prior family planning clinic visits, having a primary care provider, prior pregnancy, and prior use of contraceptives, potentially confound or modify the effect of texting on contraception initiation. We will also examine texting response rates over time and how this relates to contraception initiation. We will also measure changes in contraception knowledge and decisional conflict based on proportions.

Sample size: Using prior ED studies, we expect to enroll approximately 250 patients over 2 years. Accounting for a 20% lost to follow up rate, this would enable us to detect a 17% absolute increase in contraception initiation

(assuming 17% in SR arm, based on prior data) with 80% power ( $p=0.05$ , two sided). We readily understand that the effect size is likely not to be this large. As this is a pilot trial (Phase II), our goal is to gather the preliminary data needed for a definitive, multi-center RCT grant application (Phase III). We also plan to enroll equal proportions of younger (aged 14-17) and older (aged 18-19) adolescents to verify our prior findings that age modifies the effect of the intervention, with younger teens more often initiating contraceptives than older teens.

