## Study Procedures

Eligible enrolled patients will either text message in the ED will confirm intervention receipt (manual enrollment) or will text RipRoad for enrollment (technological enrollment). This will ensure texting capabilities.

10 participants will receive the 2 month intervention as a beta test. They will receive weekly follow-up calls to qualitatively assess real-life occurrences, such as current sexual activity, change in pregnancy intentions, and perspectives of the messages. Questions will include, “*What about the program is least or most engaging?*” and “*How have your contraceptive choices change because of the texts?*”.

Other probes may include questions about message frequency and time of day. Texts will then be refined and finalized. 40 participants will receive the complete intervention to assess feasibility and acceptability, and potential effectiveness. These participants will not be assessed weekly but rather 3 months after enrollment (week 12).

We expect that approximately 10 of the 50 participants will have technological issues with their phones such as phone disconnections. That is why we have a target accrual of 50 but an actual accrual of 40.

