### **Statistical Analysis**

For the first 10 participants, we will measure acceptability of the program via weekly follow-up phone calls. (See Documents) Questions include which messages the participants liked the best, the least, and why.

For the following 90 participants, we will summarize data using standard descriptive statistics.

Feasibility of the program will be determined by measuring the proportion of those eligible who are enrolled, the lost to follow up and opt out rates, and the texting response rates (as an indicator of engagement). We will summarize technological problems such as bounced back messages by proportions.

Acceptability will be determined after the intervention via web-based surveys (assessing satisfaction using a 5 point Likert scale and free-text responses) and telephone follow-up (including open ended questions regarding message satisfaction).

Outcomes will be measured at month 3, which is 2 weeks after the completion of the 10-week intervention. We will assess the primary patient-oriented outcome of whether the participant initiated effective contraception based on EMR review and self-report. We will consider “effective contraception initiated” if (1) patient self-reports initiation or (2) there is EMR documentation of initiation. We define “effective contraception not initiated” if noted by self-report to not have initiated, or lost to follow-up and no evidence of initiation in EMR.

Another outcome is decisional conflict. This measures a participant’s level of commitment to choosing a birth control method and has been used in other contraceptive studies and is a validated scale. We are using the low literacy version to meet the needs of our adolescent population.

We will also conduct exploratory analyses to identify characteristics of participants who appear more likely to opt out of the study (allowing us to develop further retention strategies). Finally, we will examine texting response rates over time and how this relates to contraception initiation. Secondary outcomes include follow-up to reproductive care clinics, pregnancy rates, an increase in condom use, talking to an adult about birth control, and psychosocial mediators of behavior change.

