#### Study Procedures: (different than Part 1)

After a patient provides informed consent, participants will complete a baseline questionnaire (new version attached as a Document, which is a shorter version of Part 1 baseline questionnaire).

Participants will then be block-randomized into one of two arms, Text Messaging (TM) or Standard Referral (SR). Participants will receive a \$10 gift card.

After randomization, participants in the TM arm will receive the texting intervention. The server will store all libraries of branched-logic messages and responses. All ingoing and outgoing texts will be time-stamped, recorded, and accessible to investigators.

Patients randomized to the SR arm will receive a welcome text message and then standard medical care as decided by their emergency medicine physician.

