  - In our prior qualitative interviews, we learned that adolescents receive their health information from unreliable sources, especially on the Internet. We created [www.dr-erica.com](http://www.dr-erica.com) as a one-stop website that contains reliable, medically accurate links to websites such as StayTeen.org and Bedsider.org. Topics include birth control options, local clinics, testimonials, and an introduction to who Dr.Erica is. Many of the links we sent to teens in our texts are on this site. This site contains NO Columbia identifiers, collects NO patient identifiers, and is approved by Columbia University Information Technology.

- (NEW TO THIS MODIFICATION): We will be asking for email addresses for the following two reasons:
  - Disconnected phone numbers: Adolescents often change phone numbers. If RipRoad reports that a phone number has “undelivered” texts, that is usually due to a disconnected phone number. We will email that participant (using the email template attached in Documents) to ask for an updated phone number.
  - Follow up: If a participant does not complete the follow up survey (sent via text as a link), she will be sent an email with the follow-up survey link (using the email template attached in Documents).
- All text messages are attached under Documents.
- Based on preliminary feedback from Study Part 1, we found that many adolescent text questions into the program such as “Where can I get birth control pills?”. Because this program is automated, when questions are received, we send an error message that reads, “Sorry, we do not understand that. If you are answering a question, please reread & try again. If you have general questions, check out [www.dr-erica.com](http://www.dr-erica.com).” Therefore, these questions are never answered by the program. As a solution to this, we have built in “[name] Hours.” This will work in the following manner:
  - Any incoming response (text into the program by a participant) that is 4 or more words will trigger two events:
    - A response text to the participant which reads as follows: “Sorry, I don’t understand your text. But we can answer your questions LIVE during our [name] Hours. You can text privately with a confidential health educator who can answer all your questions! [name] Hours are from 7-8pm. I’ll have her text you this week and let you both connect. In the meanwhile, check out dr-erica.com.”

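### The Part 2 bounce-back rate is a proportion of texts, but the number of texts can depend on whether the phone works, so it can understate the share of participants whose phones fail.

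*Combined protocol and SAP*

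**What the plan says.** Part 2, Outcomes and Data Sources, lists six feasibility measures. Item (d) is "technological failures (frequency and proportion of text message" bounce-backs, expected below 20%. Item (e) is "response to texting interactivity, as an indicator of engagement", expected above 80%, with no numerator or denominator given. Opt-outs are counted separately in item (b) as "opt outs (texted to stop receiving messages", expected below 5%. The data are to come from the mobile platform provider. The Analysis paragraph plans only descriptive statistics for feasibility. Part 1, Statistical Analysis, takes the same line: "We will summarize technological problems such as bounced back messages by proportions".

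On how texts are generated, Part 2, Study Procedures, says: "The server will store all libraries of branched-logic messages and responses". Part 2, Sources of material, adds: "Any incoming response (text into the program by a participant) that is 4 or more words will trigger two events". One event is an automatic text back to the participant. The other is an alert that leads to a live text exchange.

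On failing phones, the same section says: "If RipRoad reports that a phone number has “undelivered” texts, that is usually due to a disconnected phone number". The participant is then emailed for a new number. The protocol does not say whether scheduled texts continue to go to the old number, or how they count. Part 1, Study Procedures, gives the only expected participant-level figure: "We expect that approximately 10 of the 50 participants will have technological issues with their phones such as phone disconnections".

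**The concern.** A proportion of texts is a natural measure when everyone is sent the same number. The earlier pilot came close to that, because its texts were one-way and the number sent did not depend on replies. Part 2 differs. A participant who texts in can be sent further messages; a disconnected phone cannot prompt any. The denominator of item (d) can therefore depend on the very thing being measured, with working phones given more weight than failed ones.

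What the trial team needs to know is how many randomised TM participants the programme failed to reach. Feasibility is part of the Part 2 hypothesis, and the section on the importance of the knowledge to be gained says the study's data will inform whether to proceed to a larger multi-center trial. A text-level rate can meet the expectation of less than 20% when the participant-level rate does not. It could also look better than the pilot's rate only because interactivity added texts to phones that already worked.

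**Working it through.** **The documents' own figure.** Preliminary Studies reports 1172 of 1654 pilot texts delivered: 1172/1654 = 70.9%, so 29.1% were not delivered. This reproduces, and it is a per-text rate.

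**Inputs for item (d).**
- d, the share of TM participants whose phone does not work. I take 10/50 = 20% from Part 1, Study Procedures. That figure covers phone problems in general, so using it for non-working phones is an assumption.
- k, the number of texts sent to a working phone divided by the number sent to a non-working one. The documents do not give it, because the algorithms are in attachments. I show a range.
- Simplification: every text to a non-working phone bounces and none to a working phone does.

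**Formula.** Pooled bounce rate = d / (d + (1 − d)k).

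| k | Calculation at d = 0.20 | Pooled rate | Participant rate |
|---|---|---|---|
| 1 | 0.20/1.00 | 20.0% | 20% |
| 1.25 | 0.20/1.20 | 16.7% | 20% |
| 1.5 | 0.20/1.40 | 14.3% | 20% |
| 2 | 0.20/1.80 | 11.1% | 20% |
| 3 | 0.20/2.60 | 7.7% | 20% |

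For k of 1 or more, the pooled rate never exceeds the participant rate.

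**How much failure the 20% expectation could hide.** Setting the pooled rate to 0.20 gives k = 4d/(1 − d). At k = 2 this gives d = 1/3, so up to a third of phones could be dead before the pooled rate reached 20%. If the pilot's 29.1% is assumed to be a participant-level rate, k = 4 × 0.2914/0.7086 = 1.645. Above that ratio the pooled figure drops below 20% although no more phones work.

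**Item (e).** Suppose 60% of participants reply (r = 0.6) and silent participants are sent one text per session. Two ways of counting give different answers.

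| k | Responders answer all k texts: rk/(rk + 1 − r) | Each exchange ends in one unanswered closing text: r(k − 1)/(rk + 1 − r) |
|---|---|---|
| 2 | 1.2/1.6 = 75.0% | 0.6/1.6 = 37.5% |
| 3 | 1.8/2.2 = 81.8% | 1.2/2.2 = 54.5% |
| 4 | 2.4/2.8 = 85.7% | 1.8/2.8 = 64.3% |

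Against a true 60%, the first count is too high throughout. The second is too low at k = 2 and 3, and slightly too high at k = 4. Without a stated denominator, neither the size nor the direction can be fixed.

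**The case against.** The strongest objection is that the mechanism rests on material not in the documents. Branched logic may change which message is sent without changing how many. The only extra texts actually described are the automatic response to longer incoming texts and the live exchange, and nothing says that either enters the denominator. If they are few, or excluded, k is near 1 and the bias is negligible. This stands, and it is why the conclusion is conditional.

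Participants with undelivered texts are also pursued by email for a new number, so a phone that is dead for the whole programme is the worst case. That stands too. The per-text rate matches the pilot's metric, which is a good reason to keep it but not to report it alone.

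Participant-level information is partly implied already. The per-protocol population excludes TM participants who received no texts, and response rates are to be related to contraception initiation, which is a participant outcome. This shows that the summary is within reach, but no participant-level version of item (d) is specified.

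A reader might infer that reply rates are also pooled over texts and therefore inflated. The documents do not say so: item (e) has no denominator, and the second count above can reverse the direction. A reader might also expect reply rates to rise over time as disengaged participants opt out. That is not shown. Opt-outs are a separate outcome expected below 5%. Even if 5% left at once and the rest answered 80% of prompts, the all-participant rate would be 0.95 × 80% = 76%, a gap of 4 points.

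**Conclusion.** The point holds for item (d), conditionally. The bounce-back rate is defined per text, the number of texts can depend on a working phone and on replies, and no participant-level rate is specified. If working phones are sent more texts than failed ones, the pooled rate understates participant-level failure. With 20% of phones not working it reads 14.3% at k = 1.5, 11.1% at k = 2 and 7.7% at k = 3; at k = 1 there is no bias. The size rests on the assumed k, on applying the Part 1 expectation to non-working phones, and on each phone either failing or working throughout.

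For item (e), the supportable conclusion is only that the denominator is undefined.

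It would go too far to conclude that engaged phones dominate the counts or that feasibility as a whole is overstated. Texts per participant are not given, one of six measures is clearly affected and a second possibly so, and both are descriptive expectations, not formal criteria for proceeding. The primary efficacy outcome is not touched. This is a cheap improvement worth making, not a flaw that threatens the trial.

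**What to change.** Define the numerator and denominator of both measures in the Part 2 Outcomes and Analysis paragraphs.

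- **Item (d):** report the proportion of all randomised TM participants with any non-delivery of scheduled texts, and the proportion with persistent non-delivery, with persistence defined in advance. Keep the pooled per-text rate alongside for comparison with the pilot.
- **Item (e):** for each participant, calculate the share of scheduled, reply-requesting prompts that were answered, and summarise these shares over all randomised TM participants. Count prompts due after opt-out as unanswered, and show undelivered prompts separately.
- **Both:** leave automatic triggered replies and live-hours texts out of these scheduled-text denominators, and state how scheduled texts to a number already known to be disconnected are counted.

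No new data are needed, because Part 2, Study Procedures, already has every text recorded and time-stamped. The cost is a little more analysis and possibly less favourable figures.

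### Scoring the lost as not initiated is conservative only if the texting arm is ascertained no better than standard referral, and the undefined self-report by text leaves that open

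*Combined protocol and SAP*

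**What the plan says.** All references are to the combined protocol and SAP, Part 2.

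- **Outcome.** In Outcomes and Data Sources, the Efficacy paragraph counts initiation if "patient self-reports initiation at phone follow up or via text" or if the EMR documents it. Self-report prevails where the two disagree; the example given is a prescription received but pills never started. Participants who are lost, with nothing in the EMR, count as not initiated. The paragraph gives no window, no EMR cut-off and no list of qualifying texts.
- **Nearby timing.** The preceding paragraph, on acceptability, collects data during month 3 "via phone follow up and web-based survey sent via text message link". A later sentence reads "Data for secondary outcomes will also be collected via phone follow up and EMR review during month 3" and adds "interactive text messaging at weeks 3 and 6", without saying which arm receives those texts.
- **Contact by arm.** Under Study Procedures, "participants in the TM arm will receive the texting intervention", and "All ingoing and outgoing texts will be time-stamped, recorded, and accessible to investigators". For the other arm: "Patients randomized to the SR arm will receive a welcome text message and then standard medical care".
- **Safeguards.** Sources of material describes follow-up calls and an email fallback that begins "If a participant does not complete the follow up survey (sent via text as a link"; it is not limited to one arm.
- **Analysis.** In the ITT analysis the lost are imputed as not initiated, described as conservative. The per-protocol set keeps those who completed follow-up and drops TM participants who received no texts. No analysis under another missing-data assumption is given.

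**The concern.** Scoring the lost as failures protects against a false claim only when the experimental arm loses at least as many participants as control. If TM is captured more fully, the same rule removes more real initiations from SR than from TM and can create an apparent benefit.

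Two features of the plan leave this possible. First, the wording of the self-report route would let an initiation volunteered inside the two-way programme count, and that programme is described only for TM. Second, the email asking for a new phone number is triggered by undelivered texts, and ten weeks of messages give more chances to discover a dead number than the SR contact that is described.

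The pilot is meant to feed a definitive multi-centre application, and the Sample size paragraph itself expects an effect below 17 points. A shift of a point or two from ascertainment alone would then weigh more in planning than it does against the nominal target.

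**Working it through.** **Inputs from the plan.** 250 enrolled; 17% initiation in SR; 17-point increase; 20% loss, with no split by arm; two-sided 0.05; 80% power; chi-square test. Allocation is not stated; 1:1 is assumed, giving 125 per arm.

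**The plan's own figure.** 250 × 0.8 / 2 = 100 evaluable per arm. For 17% against 34% with pooled variance, power = Φ{[0.17 − 1.96√(2 × 0.255 × 0.745/100)] / √[(0.17 × 0.83 + 0.34 × 0.66)/100]} = 79.2%, which agrees with the stated 80%. The sample size is not in question.

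**Model with no true effect.** Let *r* be the share of an arm whose self-report is captured and *e* the share of missed initiators found in the EMR. With no false reports and loss unrelated to initiation, observed rate = 0.17 × [*r* + (1 − *r*) × *e*]. Capture by arm and *e* are assumptions. Rejection rates come from exact binomial enumeration of the uncorrected chi-square test at 125 per arm.

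| TM / SR captured | *e* | TM / SR observed | Shift (points) | Rejection (for TM / for SR) |
|---|---|---|---|---|
| 80% / 80% | 0 | 13.6% / 13.6% | 0 | 4.8% (2.4 / 2.4) |
| 90% / 80% | 0 | 15.3% / 13.6% | +1.7 | 6.4% (5.5 / 0.9) |
| 100% / 80% | 0 | 17.0% / 13.6% | +3.4 | 11.2% (10.9 / 0.3) |
| 70% / 80% | 0 | 11.9% / 13.6% | −1.7 | 6.7% (0.9 / 5.8) |
| 90% / 80% | 0.5 | 16.15% / 15.3% | +0.85 | 5.2% (3.6 / 1.5) |
| 100% / 80% | 0.5 | 17.0% / 15.3% | +1.7 | 6.3% (5.3 / 1.0) |
| 100% / 88% | 0 | 17.0% / 14.96% | +2.0 | 7.0% (6.2 / 0.8) |
| 100% / 88% | 0.5 | 17.0% / 15.98% | +1.0 | 5.3% (3.9 / 1.4) |

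The 88% is the overall follow-up in the team's earlier pilot (Preliminary Studies), applied here to SR as an assumption.

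**Effect of self-report overriding the EMR.** Let *f* be the share of an arm with an EMR entry who never started. If reached they count as not initiated; if lost they count as initiated. This adds (1 − *r*) × *f* to the observed rate. At 90% against 80% with *e* = 0.5, shift = 0.10 × (0.17 × 0.5 − *f*). For *f* = 0, 5%, 8.5% and 10% (assumed) this gives +0.85, +0.35, 0 and −0.15 points.

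**Does the per-protocol analysis settle it?** At 90% against 80%, with about 112 and 100 completers and loss unrelated to initiation, it compares 17% with 17% and rejects 5.0% of the time. If the lost initiate at rate *q* while the overall rate stays 17%, completer rate = [0.17 − (1 − *r*)*q*]/*r*. With no EMR recovery:

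- *q* = 8.5%: completers 17.9% against 19.1%, −1.2 points; lost scored as failures 16.15% against 15.3%, +0.85 points.
- *q* = 25%: completers 16.1% against 15.0%, +1.1 points; lost scored as failures 14.5% against 12.0%, +2.5 points.

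The two planned analyses can err in opposite directions or in the same one, so agreement or disagreement between them does not identify the bias.

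**The case against.** The benign reading is the likely one. The paragraph just before the endpoint pairs phone follow-up with a survey link sent by text; Sources of material describes that survey with an email fallback and no restriction by arm; the week-3 and week-6 texts are named for secondary outcomes; and month 3 is implied for the primary outcome. The text messages and follow-up forms attached to the protocol are not in the file and may settle which texts count. All of this stands, and it makes unequal capture a possibility and not a finding.

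A reader might infer that TM can report by text while SR cannot, so that the rule favours texting. The documents do not support that. They do not say what SR receives between the welcome text and the survey, and TM opt-outs could make TM the arm with more loss. Because self-report overrides the EMR, fuller TM capture also removes EMR-positive non-starters from TM, which can cancel or reverse the shift.

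The size is also modest. The plan expects loss below 20%, so the 80% capture rate is at the pessimistic end. At 13.6% in each arm the 95% half-width for the difference is 1.96 × √(2 × 0.136 × 0.864/125) = 8.5 points, far wider than any shift above. Phone calls, the emailed link and EMR review narrow the gap further.

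What remains is that the conservative label is unconditional when the property is not, and that the endpoint wording does not exclude a route described for one arm only.

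**Conclusion.** The point holds as a minor one. Imputing failure for the lost is conservative for claiming efficacy only when TM ascertainment is no better than SR, and the plan neither secures nor checks this. Even when TM loses more, the rule protects against a false claim only by biasing the estimate downward.

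Under the assumed 90% against 80% capture the shift is +1.7 points with 6.4% rejection, or +0.85 points with 5.2% if the EMR finds half of the missed initiators. With SR at 88%, the ceiling is +2.0 points and 7.0%. The +3.4 points in the table needs complete TM capture, 20% SR loss and no EMR recovery. All of these figures assume 17% initiation in both arms, 1:1 allocation and no EMR-positive non-starters. The actual direction cannot be known in advance. This is not a flaw in the design, and it does not show that the trial would favour texting.

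**What to change.** 1. In the Efficacy paragraph, define the primary outcome identically in both arms: the month-3 survey answer (text or email link) or phone answer, plus EMR documentation up to one stated cut-off. State that texts only one arm can send do not count.
2. Report follow-up by arm. In the Analysis paragraph, replace *conservatively* with a statement that the direction of the lost-as-failure rule depends on relative ascertainment.
3. Add one sensitivity analysis for the lost: either an arm-specific tipping point, or multiple imputation using arm, age group and baseline covariates.

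Keep the planned week-3 and week-6 secondary data, and compare them between arms only if both arms supply them.

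The cost is a few sentences and one extra analysis. The downside is that a few TM initiations reported only by programme text will not be counted.

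### The retention analysis looks at who opts out of texts, an event expected in under 5%; loss to follow-up, expected in up to 20%, gets no analysis of participant characteristics

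*Combined protocol and SAP*

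**What the plan says.** Under Part 2, Outcomes and Data Sources, the feasibility outcomes include "opt outs (texted to stop receiving messages", expected in under 5%, and, as a separate item, loss to follow-up, expected in under 20%. No denominator is given for the opt-out rate.

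The Analysis paragraph in the same section summarises feasibility outcomes descriptively and adds one analysis of participant characteristics: it will "conduct exploratory bivariable analyses to identify characteristics of participants who appear more likely to opt out of the study". The stated purpose is to develop further retention strategies. A similar sentence appears earlier in the section. Neither mentions loss to follow-up.

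The Sample size paragraph says "we expect to enroll approximately 250 patients over 2 years" and continues: "Accounting for a 20% lost to follow up rate, this would enable us to detect a 17% absolute increase in contraception initiation".

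In the same section, the primary outcome may come from self-report by phone or text, or from the medical record. Participants who are lost and have no record of initiation count as not having initiated. The per-protocol population is limited to those who completed follow-up.

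**The concern.** The analysis is meant to inform retention, but the outcome it uses is not retention. A participant who stops the texts can still be reached by phone or traced in the medical record. One who never texts to stop can still be lost, for example through a disconnected phone, which the Part 2 Sources of material section describes as common. The term also shifts: the feasibility list defines opting out as stopping messages, while the analysis speaks of opting out of the study.

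The chosen event is also the rarer of the two at the plan's own rates, so a real predictor will probably be missed and an apparent one may well be chance.

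Loss to follow-up is what affects the efficacy analysis. It leads to imputed non-initiation in the intention-to-treat population and exclusion from the per-protocol population, in both arms. The Sample size paragraph says the pilot is to supply preliminary data for a multi-center trial. Knowing who is lost would be useful for that purpose.

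**Working it through.** **Inputs from the plan.** About 250 randomised; two arms, block-randomised (Study Procedures, Part 2); opt-outs under 5%; loss under 20%, set at 20% for sample size; 17% initiation in Standard Referral, 17-point increase, 80% power, two-sided 0.05. Follow-up in the earlier pilot trial was 88%, so 12% were lost (Preliminary Studies).

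**Assumptions.** Allocation is 1:1 (ratio not stated), so 125 per arm. One binary characteristic is held by half the participants. Two-sided Fisher exact test at 5%, with no allowance for testing several characteristics.

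**The plan's own figure first.** With 17% v 34% and unpooled variance:

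n per arm = (1.960 + 0.842)² × (0.17×0.83 + 0.34×0.66) / 0.17² = 7.849 × 0.3655 / 0.0289 = 99.3, so 100.

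That gives 200 evaluable, and 200 / (1 − 0.20) = 250. The sample size reproduces, and 20% loss is built into it.

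**Expected events.**
- Opt-outs, texting arm as denominator: 0.05 × 125 = 6.25, about 6.
- Opt-outs, everyone as denominator: 0.05 × 250 = 12.5, about 12.
- Loss at 20%: 0.20 × 250 = 50, the upper end of the plan's expectation.
- Loss at 12%: 0.12 × 250 = 30.

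These are expected counts, not ceilings. At a true 5% rate, the binomial probability of 7 or more opt-outs among 125 is 0.43.

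**What six events can show.** Split 125 into 62 and 63. Only a 6–0 split reaches p<0.05 (p = 0.013 or 0.028, depending on which group holds the events). A 5–1 split gives p = 0.11 or 0.21.

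**Power.** For overall rate m and a k-fold difference between equal halves, the lower rate is 2m/(1+k) and the higher is k times that. At m = 5% and k = 2 the rates are 3.33% and 6.67%; at k = 3 they are 2.5% and 7.5%. Exact Fisher power:

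| Outcome and denominator | Expected events | Twofold | Threefold |
|---|---|---|---|
| Opt-out, texting arm (62 v 63) | about 6 | 5–9% | 11–17% |
| Opt-out, all randomised (125 v 125) | about 12 | 14% | 32% |
| Loss 20%, both arms (125 v 125) | 50 | 71% | 97.5% |
| Loss 12%, both arms (125 v 125) | 30 | 42% | 80% |

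The ranges in the first row depend on whether the higher rate falls in the group of 62 or of 63. The same test is used in every row.

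**The case against.** The strongest reply is that the plan labels this analysis exploratory, in a pilot, with no decision rule resting on it. Loss to follow-up is already reported as a feasibility outcome, and the intention-to-treat rule deals with it in the primary analysis. Who stops the messages is also a proper question for a texting programme. All of this stands. It keeps the point small, and it is why the opt-out summary should be kept rather than replaced.

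A second reply is that opting out of the study might mean withdrawal, not stopping texts. That reading is possible, but the only definition given is stopping messages. Under either reading loss to follow-up is not analysed by participant characteristics, and the term needs defining.

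A third is that no month-3 self-report is a new definition of loss. The plan does not define loss explicitly. However, its rule for participants who are lost and have no evidence in the record treats loss as something established apart from the record, so this definition fits.

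A reader might also infer that the plan expects at most six opt-outs, and only in the texting arm. The documents do not support that. They give no denominator and no allocation ratio. Standard Referral participants receive a welcome text, and the texted survey link and the week 3 and 6 texts are not limited to one arm.

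**Conclusion.** The point holds as a minor improvement. The only analysis of characteristics intended for retention uses an event that is not loss and, at the planned rates, is 4 to 8 times rarer (50/12.5 and 50/6.25). Its power is about 5–14% for a twofold difference and 11–32% for a threefold difference. Loss to follow-up in both arms gives about 71% and 97.5% at 20% loss, or 42% and 80% at 12%.

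These figures rest on 1:1 allocation, one evenly split characteristic and no multiplicity adjustment. Uneven characteristics, or several of them tested with adjustment, would lower the power.

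It would go too far to conclude that the planned analysis cannot find anything, or that analysing loss would identify who needs retention effort. A very marked opt-out pattern could still show. At 12% loss, a twofold difference is more likely to be missed than found.

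**What to change.** In Part 2, Outcomes and Data Sources, including its Analysis paragraph:

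- Apply the exploratory retention analysis to loss to follow-up, defined as no month-3 self-report obtained, in both arms, with arm in the model.
- Keep opt-outs as a separate feasibility outcome, labelled as opted out of texts. State the denominator, report the count with an interval, and describe those who opted out by their characteristics.
- Use the two terms consistently, so that stopping texts is not described as leaving the study.

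This uses data the trial already plans to collect. It costs a change of wording and a little more exploratory analysis. Only fairly strong associations will be detectable, and the report should say so.
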